13.2.1 Method

This study will be monitored by the Clinical Trials Monitoring Service (CTMS). Data will be submitted to CTMS at least once every two weeks via Medidata Rave (or other modality if approved by CTEP). Information on CTMS reporting is available at <http://www.theradex.com/clinicalTechnologies/?National-Cancer-Institute-NCI-11>. On-site audits will be conducted three times annually (one annual site visit and two data audits). For CTMS monitored studies, after users have activated their accounts, please contact the Theradex Help Desk at [contact] or by email at [contact] for additional support with Rave and completion of CRFs.

13.2.2 Responsibility for Data Submission

For ETCTN trials, it is the responsibility of the PI(s) at the site to ensure that all investigators at the ETCTN Sites understand the procedures for data submission for each ETCTN protocol and that protocol specified data are submitted accurately and in a timely manner to the CTMS via the electronic data capture system, Medidata Rave.

Data are to be submitted via Medidata Rave to CTMS on a real-time basis, but no less than once

every 2 weeks. The timeliness of data submissions and timeliness in resolving data queries will be tracked by CTMS. Metrics for timeliness will be followed and assessed on a quarterly basis. For the purpose of Institutional Performance Monitoring, data will be considered delinquent if it is greater than 4 weeks past due.

Data from Medidata Rave and CTEP-AERS is reviewed by the CTMS on an ongoing basis as data is received. Queries will be issued by CTMS directly within Rave. The queries will appear on the Task Summary Tab within Rave for the CRA at the ETCTN to resolve. Monthly web-based reports are posted for review by the Drug Monitors in the IDB, CTEP. Onsite audits will be conducted by the CTMS to ensure compliance with regulatory requirements, GCP, and NCI policies and procedures with the overarching goal of ensuring the integrity of data generated from NCI-sponsored clinical trials, as described in the ETCTN Program Guidelines, which may be found on the CTEP

(http://ctep.cancer.gov/protocolDevelopment/electronic_applications/adverse_events.htm) and CTSU websites.

CTMS will utilize a core set of eCRFs that are Cancer Data Standards Registry and Repository (caDSR) compliant (<http://cbiit.nci.nih.gov/ncip/biomedical-informatics-resources/interoperability-and-semantics/metadata-and-models>). Customized eCRFs will be included when appropriate to meet unique study requirements. The PI is encouraged to review the eCRFs, working closely with CTMS to ensure prospectively that all required items are appropriately captured in the eCRFs prior to study activation. CTMS will prepare the eCRFs with built-in edit checks to the extent possible to promote data integrity.

CDUS data submissions for ETCTN trials activated after March 1, 2014, will be carried out by the CTMS contractor, Theradex. CDUS submissions are performed by Theradex on a monthly basis. The trial's lead institution is responsible for timely submission to CTMS via Rave, as above.

Further information on data submission procedures can be found in the ETCTN Program Guidelines
(http://ctep.cancer.gov/protocolDevelopment/electronic_applications/adverse_events.htm).

13.3 Data Quality Portal

The Data Quality Portal (DQP) provides a central location for site staff to manage unanswered queries and form delinquencies, monitor data quality and timeliness, generate reports, and review metrics.

The DQP is located on the CTSU members' website under Data Management. The Rave Home section displays a table providing summary counts of Total Delinquencies and Total Queries. DQP Queries, DQP Delinquent Forms, DQP Form Status and the DQP Reports modules are available to access details and reports of unanswered queries, delinquent forms, forms with current status and timeliness reports. Review the DQP modules on a regular basis to manage specified queries and delinquent forms.

The DQP is accessible by site staff that are rostered to a site and have access to the CTSU website. Staff that have Rave study access can access the Rave study data using a direct link on the DQP.

To learn more about DQP use and access, click on the Help icon displayed on the Rave Home, DQP Queries, DQP Delinquent Forms, DQP Form Status, and DQP Reports modules.

APPENDIX A PERFORMANCE STATUS CRITERIA

ECOG Performance Status Scale		Karnofsky Performance Scale	
Grade	Descriptions	Percent	Description
0	Normal activity. Fully active, able to carry on all pre-disease performance without restriction.	100	Normal, no complaints, no evidence of disease.
		90	Able to carry on normal activity; minor signs or symptoms of disease.
1	Symptoms, but ambulatory. Restricted in physically strenuous activity, but ambulatory and able to carry out work of a light or sedentary nature (e.g., light housework, office work).	80	Normal activity with effort; some signs or symptoms of disease.
		70	Cares for self, unable to carry on normal activity or to do active work.
2	In bed <50% of the time. Ambulatory and capable of all self-care, but unable to carry out any work activities. Up and about more than 50% of waking hours.	60	Requires occasional assistance, but is able to care for most of his/her needs.
		50	Requires considerable assistance and frequent medical care.
3	In bed >50% of the time. Capable of only limited self-care, confined to bed or chair more than 50% of waking hours.	40	Disabled, requires special care and assistance.
		30	Severely disabled, hospitalization indicated. Death not imminent.
4	100% bedridden. Completely disabled. Cannot carry on any self-care. Totally confined to bed or chair.	20	Very sick, hospitalization indicated. Death not imminent.
		10	Moribund, fatal processes progressing rapidly.
5	Dead.	0	Dead.

APPENDIX B FORMULA TO ESTIMATE RENAL FUNCTION USING SERUM CREATININE

Formulas to estimate renal function using serum creatinine provided by the NCI's Investigational Drug Steering Committee (IDSC) Pharmacological Task Force in table below.

1. Estimated glomerular filtration rate (eGFR) using the Chronic Kidney Disease Epidemiology Collaboration (CKD-EPI) (Levey *et al.*, 2009).

Formulae:

Race and Sex	Serum Creatinine (SCr), $\mu\text{mol/L (mg/dL)}$	Equation
Black	Female $\leq 62 (\leq 0.7)$	$\text{GFR} = 166 \times (\text{SCr}/0.7)^{-0.329} \times (0.993)^{\text{Age}}$
	$> 62 (> 0.7)$	$\text{GFR} = 166 \times (\text{SCr}/0.7)^{-1.209} \times (0.993)^{\text{Age}}$
	Male $\leq 80 (\leq 0.9)$	$\text{GFR} = 163 \times (\text{SCr}/0.9)^{-0.411} \times (0.993)^{\text{Age}}$
	$> 80 (> 0.9)$	$\text{GFR} = 163 \times (\text{SCr}/0.9)^{-1.209} \times (0.993)^{\text{Age}}$
White or other	Female $\leq 62 (\leq 0.7)$	$\text{GFR} = 144 \times (\text{SCr}/0.7)^{-0.329} \times (0.993)^{\text{Age}}$
	$> 62 (> 0.7)$	$\text{GFR} = 144 \times (\text{SCr}/0.7)^{-1.209} \times (0.993)^{\text{Age}}$
	Male $\leq 80 (\leq 0.9)$	$\text{GFR} = 141 \times (\text{SCr}/0.9)^{-0.411} \times (0.993)^{\text{Age}}$
	$> 80 (> 0.9)$	$\text{GFR} = 141 \times (\text{SCr}/0.9)^{-1.209} \times (0.993)^{\text{Age}}$

SCr in mg/dL; Output is in mL/min/1.73 m² and needs no further conversions.

2. eGFR using the Modification of Diet in Renal Disease (MDRD) Study (Levey *et al.*, 2006).

$175 \times \text{SCr}^{-1.154} \times \text{age}^{-0.203} \times 0.742$ (if female) $\times 1.212$ (if black)
 Output is in mL/min/1.73 m² and needs no further conversions.

3. Estimated creatinine clearance (ClCr) by the Cockcroft-Gault (C-G) equation (Cockcroft and Gault, 1976).

[figure not shown]
$$\text{ClCr (mL/min)} = \frac{[140 - \text{age (years)}] \times \text{weight (kg)}}{72 \times \text{serum creatinine (mg / dL)}} \times 0.85 \text{ for female patients}$$

Followed by conversion to a value normalized to 1.73 m² with the patient's body surface area (BSA).

References

1. Levey, A.S., L.A. Stevens, C.H. Schmid, *et al.* (2009). A new equation to estimate glomerular filtration rate. *Ann Intern Med.* 150:604-612.
2. Levey, A.S., J. Coresh, T. Greene, *et al.* (2006). Using standardized serum creatinine values in the modification of diet in renal disease study equation for estimating glomerular filtration rate. *Ann Intern Med.* 145:247-254.

APPENDIX C **PATIENT CLINICAL TRIAL WALLET CARD**

APPENDIX D **PATIENT MEDICATION DIARY**

CTEP-assigned Protocol # 10410
Local Protocol # TBD

PATIENT'S MEDICATION DIARY – IPdR

Today's date: _____ **Agent:** IPdR
Patient Name: _____ *(initials acceptable)* **Patient Study ID:** _____

INSTRUCTIONS TO THE PATIENT:

1. Complete one form for the study.
2. You will take your dose of IPdR at the same time, once a day each day, 7 days a week, until your radiation therapy is complete.

____ 75 mg capsule(s); (and) ____ 600 mg capsule(s)

You should take IPdR on an empty stomach, either 1 hour before or 2 hours after meals.

On Days 8, 21, and 35, you will receive instructions about the time you should take your IPdR, depending on the schedule of your radiation.

3. On the days of radiation therapy, the dose of IPdR should be taken within 30 min - 2 hours prior to radiation. You can take this at home as time allows.
4. Store IPdR capsules in the original bottle in the refrigerator. Record the date, the number of capsules you took, and when you took them.
5. If you forget to take a dose at the scheduled time, you can still take that dose as long as it is within 4 hours of the scheduled time. If not within 4 hours, take your next dose at the regularly scheduled time.
6. If you vomit after taking a dose, do not retake the dose. Take the next dose at the regularly scheduled time.
7. Notify your doctor at the first sign of poorly formed or loose stools, or an increased frequency of bowel movements. Loperamide (Imodium) should be kept on hand and should be taken as recommended by your doctor.
8. If you have any comments or notice any side effects, please record them in the Comments column.
9. Please remember to bring this diary (all pages) and your IPdR containers (even if they are empty) to each visit with your study team.

Day	Date	What time was dose taken?	# of Capsules taken		Comments
			75mg	600mg	
1.					
2.					
3.					
4.					
5.					
6.					
7.					
8.					
9.					
10.					
11.					
12.					
13.					
14.					
15.					
16.					
17.					
18.					
19.					
20.					
21.					
22.					
23.					
24.					
25.					
26.					
27.					
28.					

INSTRUCTIONS TO THE PATIENT:

1. Complete one form for the study.
2. You will take your dose of IPdR at the same time, once a day each day, 7 days a week, until your radiation therapy is complete.

____ 75 mg capsule(s); (and) ____ 600 mg capsule(s)

You should take IPdR on an empty stomach, either 1 hour before or 2 hours after meals.

On Days 8, 21, and 35, you will receive instructions about the time you should take your IPdR, depending on the schedule of your radiation.

3. On the days of radiation therapy, the dose of IPdR should be taken within 30 min - 2 hours prior to radiation. You can take this at home as time allows.
4. Store IPdR capsules in the original bottle in the refrigerator. Record the date, the number of capsules you took, and when you took them.
5. If you forget to take a dose at the scheduled time, you can still take that dose as long as it is within 4 hours of the scheduled time. If not within 4 hours, take your next dose at the regularly scheduled time.
6. If you vomit after taking a dose, do not retake the dose. Take the next dose at the regularly scheduled time.
7. Notify your doctor at the first sign of poorly formed or loose stools, or an increased frequency of bowel movements. Loperamide (Imodium) should be kept on hand and should be taken as recommended by your doctor.
8. If you have any comments or notice any side effects, please record them in the Comments column.
9. Please remember to bring this diary (all pages) and your IPdR containers (even if they are empty) to each visit with your study team.

Day	Date	What time was dose taken?	# of Capsules taken		Comments
			75mg	600mg	
29.					
30.					
31.					
32.					
33.					
34.					
35.					
36.					
37.					
38.					

Physician's Office will complete this section:

1. Date patient started protocol treatment _____
2. Date patient was removed from study _____
3. Patient's planned total daily dose _____
4. Total number of capsules taken during the study (each size) _____
5. Physician/Nurse/Data Manager's Signature _____

Patient's signature:

CTEP-assigned Protocol # 10410
 Local Protocol # TBD

PATIENT'S MEDICATION DIARY – Capecitabine

Today's date: _____ Agent: Capecitabine Dose: _____
 Patient Name: _____ (initials acceptable) Patient Study ID: _____

INSTRUCTIONS TO THE PATIENT:

1. Complete one form for the study.
2. You will take your dose of capecitabine at the same time twice a day, about 12 hours apart, on Monday morning through Friday evening each week during the time you receive radiation therapy.
 ____ 150 mg tablets and ____ 500 mg tablets
 You should take capecitabine within 30 minutes after eating breakfast and dinner.
3. Store capecitabine tablets in the original bottle at room temperature. Record the date, the number of tablets you took, and when you took them.
4. If you forget to take a dose at the scheduled time, you can still take that dose as long as it is within 4 hours of the scheduled time. You should not take the missed dose if it is within 8 hours of your next scheduled dose. Take your next dose at the regularly scheduled time.
5. If you vomit after taking a dose, do not retake the dose. Take the next dose at the regularly scheduled time.
6. Notify your doctor at the first sign of poorly formed or loose stools, or an increased frequency of bowel movements. Loperamide (Imodium) should be kept on hand and should be taken as recommended by your doctor.
7. If you have any comments or notice any side effects, please record them in the Comments column.
8. Please remember to bring this diary (all pages) and your capecitabine containers (even if they are empty) to each visit with your study team.

Day	Date	What time was dose taken?		# of tablets taken (morning)		# of tablets taken (evening)		Comments
		AM	PM	150 mg	500 mg	150 mg	500 mg	
1.								
2.								
3.								
4.								
5.								
6.								
7.								
8.								
9.								
10.								
11.								
12.								
13.								
14.								
15.								
16.								
17.								
18.								
19.								
20.								
21.								
22.								
23.								
24.								
25.								
26.								
27.								
28.								
29.								
30.								
31.								
32.								
33.								

INSTRUCTIONS TO THE PATIENT:

1. Complete one form for the study.
2. You will take your dose of capecitabine at the same time twice a day, about 12 hours apart, on Monday morning through Friday evening each week during the time you receive radiation therapy.
 ____ 150 mg tablets and ____ 500 mg tablets
You should take capecitabine within 30 minutes after eating breakfast and dinner.
3. Store capecitabine tablets in the original bottle at room temperature. Record the date, the number of tablets you took, and when you took them.
4. If you forget to take a dose at the scheduled time, you can still take that dose as long as it is within 4 hours of the scheduled time. You should not take the missed dose if it is within 8 hours of your next scheduled dose. Take your next dose at the regularly scheduled time.
5. If you vomit after taking a dose, do not retake the dose. Take the next dose at the regularly scheduled time.
6. Notify your doctor at the first sign of poorly formed or loose stools, or an increased frequency of bowel movements. Loperamide (Imodium) should be kept on hand and should be taken as recommended by your doctor.
7. If you have any comments or notice any side effects, please record them in the Comments column.
8. Please remember to bring this diary (all pages) and your capecitabine containers (even if they are empty) to each visit with your study team.

Day	Date	What time was dose taken?		# of tablets taken (morning)		# of tablets taken (evening)		Comments
		AM	PM	150 mg	500 mg	150 mg	500 mg	
34.								
35.								
36.								
37.								
38.								

Physician's Office will complete this section:

1. Date patient started protocol treatment _____
2. Date patient was removed from study _____
3. Patient's planned total daily dose _____
4. Total number of capsules taken during the study (each size) _____
5. Physician/Nurse/Data Manager's Signature _____

Patient's signature:

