- a “moderate” toxicity, two additional patients will be entered at this dose level, and if
 - one of these patients develops a DLT, the stop/switch rule is invoked, and part IB commences
 - one of these patients develops a “moderate” toxicity, the stop/switch rule is invoked, and part IB commences
 - neither of the two additional patients develops a DLT or “moderate” toxicity, part IA recommences at the next dose level

A patient will be considered unevaluable if they receive $<67\%$ of their total intended dose of any study treatment (IPdR, capecitabine, or RT) for non-protocol required reasons. Patient medication diaries and RT documentation will be reviewed as each patient comes off-study to determine the actual total doses of each study treatment they received. If a patient is deemed unevaluable by this definition, they will be replaced by a new patient to be treated at the same intended dose level.

Part IA dose escalation schema			
Dose Level	Total radiation Gy (45 Gy primary field, 5.4 Gy [contact] Gy/fraction/day)	Capecitabine (mg/m² BID)	IPdR (mg BID) Administered throughout radiation
1A	50.4	825 mg/m ² BID	75 mg BID
2A	50.4	825 mg/m ² BID	150 mg BID
3A	50.4	825 mg/m ² BID	300 mg BID
4A	50.4	825 mg/m ² BID	600 mg BID
5A	50.4	825 mg/m ² BID	1,200 mg BID

BID – Twice Daily, RT – Radiation therapy

Part IA is closed to further accrual.

Part IB:

Under Part IB of this protocol, cohorts of 3-6 patients will be entered per dose level. In Part IB, 3 patients will initially be accrued to a dose level. If 0 of 3 patients do not experience grade 3 non-hematopoietic or grade 4 hematopoietic/GI DLT, then dose escalation will proceed. If a DLT is observed in one of the first 3 patients in a dose level cohort, the cohort will be expanded to a maximum of 6 patients.

Part IB dose escalation schema			
Dose Level	Total radiation Gy (45 Gy primary field, 5.4 Gy [contact] Gy/fraction/day)	Capecitabine (mg/m² BID)	IPdR (mg QD) Administered throughout radiation^{1,2}
1B	50.4	825 mg/m ² BID	75mg QD
2B	50.4	825 mg/m ² BID	150mg QD
3B	50.4	825 mg/m ² BID	300mg QD
4B	50.4	825 mg/m ² BID	600mg QD
5B	50.4	825 mg/m ² BID	1200mg QD
6B	50.4	825 mg/m ² BID	1800mg QD
7B	50.4	825 mg/m ² BID	2400mg QD

QD – Once Daily, BID – Twice Daily, RT – Radiation therapy

¹ The maximum allowed dose of IPdR is 2,400mg QD

² Actual doses will be rounded to account for availability of only 75 mg and 600 mg IPdR capsules

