Patients will be assessed 4 weeks following completion of study treatment (Week 10 unless there were delays in therapy). This will be the final assessment for study-related toxicity. Patients will undergo surgical resection 8-12 weeks following completion of chemoRT (IPdR), and study-related response will be assessed at that time.

Regimen Description					
Agent	Premedication; Precautions	Dose	Route	Schedule	Study Length
IPdR	Take on an empty stomach, either 1 hour before or 2 hours after meals.	Dose as appropriate for the assigned dose level.	PO	QD ^A	38 days (6 weeks)
Capecitabine	Take within 30 minutes after a meal (breakfast and dinner).	825 mg/m ² ^C	PO	BID Monday morning through Friday evening on RT days ^{B,C}	
RT		1.8 Gy/fraction/day × 28 doses (50.4 Gy total dose)		5 doses per week until week 5 and 3 doses during Week 6 ^D	

^AOn the days of radiation therapy, the daily dose of IPdR will be administered within 30 min - 2 hours prior to radiation. Patients may take dose at home if the timing allows.

^BCapecitabine will be taken Monday morning through Friday evening each week of RT.

^CDosing will be with 150 mg and 500 mg tablets

^DRT will be given only Monday through Friday

QD – Once Daily, BID – Twice Daily, PO – Oral, RT – Radiation therapy

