6.1.3 Capecitabine

6.1.3.1 Dose and Schedule

Capecitabine should be dosed at 825 mg/m² PO BID on days of radiation only. The usual radiation schedule will be Monday through Friday, and in that case, the first capecitabine dose of the week will be taken on Monday morning, and the last dose of the week will be taken on

Friday evening. Dosing will be with 150 mg and 500 mg tablets to achieve a dose as close as possible to 825 mg/m². Additional dose adjustments will be made as needed. At the discretion of the treating physician, the body surface area (BSA) may be capped at 2.20 – 2.25 for calculating capecitabine dosage (optional). Please refer to package insert for exact dose calculation details.

6.1.3.2 Guidance for Administration:

Capecitabine is to be taken roughly 12 hours apart at approximately the same times each day with about 200 ml of water within 30 minutes after a meal. Capecitabine tablets should be swallowed as whole and should not be crushed or cut. Capecitabine tablets should be stored at room temperature (15° to 30° C) in the container in which they are provided.

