7.2.1 Management of capecitabine for delay in radiation therapy

Capecitabine is administered BID on each day that the patient receives radiation treatment. If radiation therapy is held, no capecitabine is administered on that day. If the patient has taken the

AM capecitabine dose prior to arrival for radiation therapy, that is allowed, and the PM dose would be held. The patient should resume the AM capecitabine dose on the morning of the next scheduled radiation therapy appointment.

The duration of radiation therapy will be extended so that the total number of delivered fractions is 28 (Section 6.1). The patient should receive a minimum of 56 doses of capecitabine (BID on each day of radiation therapy and additional doses if an AM dose was taken prior to cancellation of radiation therapy for a given day).

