11. STUDY CALENDAR

Baseline evaluations are to be conducted within 1 week prior to start of protocol therapy. Scans and X-rays must be done \leq 4 weeks prior to the start of therapy. In the event that the patient's condition is deteriorating, laboratory evaluations should be repeated within 48 hours prior to

initiation of the next cycle of therapy.

NCI Protocol #: 10410
 Version Date: June 2, 2022

	Pre-Study	Wk 1	Wk 2	Wk 3	Wk 4	Wk 5	Wk 6	Wk 10 (4 wks following chemoRT) End of study for toxicity assessment	Wk 14-18 (8-12 wks following chemoRT) End of study for response assessment
IPdR		A	A	A	A	A	A		
Capecitabine		B	B	B	B	B	B		
Radiation therapy		C	C	C	C	C	C		
Surgical resection									X
mFOLFOX6 × 8 cycles	X								
Informed consent	X								
Demographics	X								
Medical history	X								
Concurrent meds	X	X	X	X	X	X	X	X	X
Physical exam	X	X	X	X	X	X	X	X	X
Vital signs	X	X	X	X	X	X	X	X	X
Height	X								
Weight	X	X	X	X	X	X	X	X	X
Performance status ^a	X	X				X		X	X
CBC w/diff, plts	X	X	X	X	X	X	X	X	X
Carcinoembryonic Antigen (CEA)	X							X	X
Comprehensive Chemistry Panel ^b	X	X	X	X	X	X	X	X	X
EKG (as indicated)	X								
Blood draws for PK and IUDR incorporation in granulocyte assays (mandatory)			X ^{c,d}	X ^{c,d}		X ^{c,d}			
Adverse event evaluation		X	X	X	X	X	X	X	
Radiologic evaluation	X								X ^e
Digital rectal exam and proctoscopic or sigmoidoscopic exam									X ^e
Pregnancy test ^f	X								

A: IPdR: Dose as assigned; PO QD administered throughout radiation (38 days, 6 weeks)
 B: Capecitabine: 825 mg/m² PO BID on days of radiation therapy (taken Monday morning through Friday evening each week of RT)
 C: Radiation therapy: 1.8 Gy/day × 28 doses (50.4 Gy total dose), M-F Days 1-5, 8-12, 15-19, 22-26, 29-33, 36-38
 a: Performance status evaluations are to be conducted every 4 weeks.
 b: Albumin, alkaline phosphatase, total bilirubin, bicarbonate, BUN, calcium, chloride, creatinine, glucose, LDH, magnesium, phosphorus, potassium, total protein, SGOT [AST], SGPT [ALT], sodium.
 c: 10 mL Blood for PK studies in sodium heparin tubes will be drawn on Day 8, prior to IPdR dose; and then after IPdR dose at 30 min, 60 min, 120 min and 240 min. On Day 21 and Day 35, blood will be drawn at 1-2 hours after the IPdR dose.
 d: 5 mL blood for measuring IUDR incorporation in granulocytes will be drawn in EDTA tubes prior to IPdR dose on Day 8, and at 1-2 hours after the IPdR dose on Day 21 and Day 35.

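### The capecitabine diary gives no instruction for weekdays without radiation, so read literally it conflicts with the RT-day rule in Sections 6.1.3.1, 7.2, 7.2.1 and 7.3, and both drug diaries stop at Day 38

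*Combined protocol and SAP*

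**What the plan says.** **Radiation-day rule.** Section 6.1.3.1 gives capecitabine "PO BID on days of radiation only. The usual radiation schedule will be Monday through Friday, and in that case" the week's doses run from Monday morning to Friday evening. Section 7.2.1 states: "If radiation therapy is held, no capecitabine is administered on that day". Its one allowance is for a patient who has already taken the "AM capecitabine dose prior to arrival for radiation therapy, that is allowed, and the PM dose would be held". Sections 7.2 and 7.3 likewise hold capecitabine when radiation is not given; 7.3 names holidays and radiation-related toxicity among the reasons. Section 7.2.1 puts the minimum number of doses at 56.

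**Patient diary.** Instruction 2 of the capecitabine diary in Appendix D tells the patient to dose "on Monday morning through Friday evening each week during the time you receive radiation therapy". No instruction covers a weekday without radiation. The rows run from Day 1 to Day 38, as they do in the IPdR diary.

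**Mixed wording.** The regimen table cell (Schema and 6.1.1) reads "BID Monday morning through Friday evening on RT days", but its footnote B drops the limit to radiation days. The second half of the Part IB dose table in the Schema has a Monday-to-Friday column header without that limit. Calendar footnote B (Section 11) gives the radiation-day rule and then adds in parentheses "taken Monday morning through Friday evening each week of RT".

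**Use of the diaries.** Section 6.1.1 says: "Patient medication diaries and RT documentation will be reviewed as each patient comes off-study to determine the actual total doses" of each study treatment. A patient who receives less than 67% of any of them for reasons not required by the protocol is replaced. Section 6.2 asks for at least 80% of planned chemoradiation doses for escalation decisions.

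**The concern.** The diary is the written instruction that the patient takes home, and weekdays without radiation are foreseen. Section 7.2 lists holidays, equipment and weather as causes of delay, accepts four treatments in a week, and lets radiation be held for toxicity. On those days the diary and the site-facing sections give different instructions.

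Capecitabine is the fixed background against which each IPdR level is judged, and Section 6.2 counts toxicities possibly or probably related to study treatment, not to IPdR alone. Capecitabine exposure that varies with how a patient reads a diary line adds unplanned variation in cohorts of 3 to 6, where a single DLT changes the escalation decision. The missing rows matter for a second reason: doses taken on make-up days have no printed place in a record that the plan uses to decide who is evaluable.

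**Working it through.** No power formula applies; this is a day count.

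**Inputs.** Radiation days are 1–5, 8–12, 15–19, 22–26, 29–33 and 36–38 (Section 11). Capecitabine is given twice daily. Missed fractions are made up at the end so that 28 are delivered (Sections 7.2 and 7.2.1). Day 1 is taken to be a Monday, as the calendar's day numbers imply.

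**The plan's own figure.** 5 × 5 + 3 = 28 radiation days, and 28 × 2 = 56 doses. This reproduces the 56 in Section 7.2.1.

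**Held weekdays.** Let h be the number of weekdays in Weeks 1–5 on which radiation is held, all made up at the end.
- Diary read literally and stopped at the last fraction: 2 × (28 + h) doses.
- Section 7.2.1: 56 doses, plus at most one already-taken morning dose per held day, so 56 to 56 + h. The upper end needs a separate late cancellation on every held day.

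| h | Last radiation day | Diary | Section 7.2.1 | Diary excess over 56 |
|---|---|---|---|---|
| 0 | 38 | 56 | 56 | 0% |
| 1 | 39 | 58 | 56–57 | 3.6% |
| 2 | 40 | 60 | 56–58 | 7.1% |
| 5 | 45 | 66 | 56–61 | 17.9% |

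Each held weekday therefore carries two doses under the diary, against 0 or 1 under 7.2.1.

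**Week 6, no holds.** There are two readings of the Monday-to-Friday wording.
- Dosing stops with the last fraction on Day 38: 28 × 2 = 56 doses, no excess.
- Dosing runs to the Friday of the last radiation week: 6 × 5 × 2 = 60 doses. The four extra doses fall on Days 39 and 40, and 4/56 = 7.1%.

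**Thresholds, if 60 were taken as the planned count** and the percentages were applied to capecitabine on its own:
- 67%: 0.67 × 56 = 37.52 and 0.67 × 60 = 40.2. A patient with 38 to 40 doses passes on one count and fails on the other.
- 80%: 0.80 × 56 = 44.8 and 0.80 × 60 = 48. The same holds for 45 to 47 doses.

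**Diary rows.** With five make-up days, 5 × 2 = 10 capecitabine doses (10/56 = 17.9%) fall after Day 38 and have no printed row. Section 7.2.2 allows up to five additional days of IPdR, which also have none.

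**The case against.** The best reply is that the site-facing text already carries the rule. The regimen cell and the full calendar footnote both limit dosing to radiation days, Section 6.1.3.1 presents Monday to Friday as the usual case, and the hold rule is repeated in 7.2, 7.2.1 and 7.3. This stands. The footnotes and the Schema header are loose shorthand beside an explicit rule, and the real gap is in the diary. Staff may well tell a patient to stop when radiation is held, but the written instruction does not say so.

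Three stronger readings are tempting, and the documents do not support them.
- *That the diary necessarily adds two days in Week 6.* Its instruction is bounded by the period of radiation, its last row is Day 38, and the regimen is 38 days long. The 60-dose count needs dosing past both the last fraction and the last row.
- *That extra capecitabine during a toxicity hold would turn the event into a DLT.* The two holding events that Section 7.2 names do not show this. Grade 4 neutropenia is already a DLT under 6.2, and grade 3 radiation dermatitis is excluded. Table 8 also holds capecitabine for neutropenia whatever the radiation status. A hold of six consecutive fractions caused by an adverse event already exceeds the limit of five in 6.2.
- *That 56 against 60 changes the denominator of the capecitabine interruption criteria in 6.2.* More than 10 consecutive or at least 19 total doses are absolute counts. Only the 67% and 80% rules are proportions.

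**Conclusion.** The point holds for the diary. Followed literally, instruction 2 gives two capecitabine doses on each held weekday, where 7.2.1 gives none or one. That is 58, 60 or 66 doses in total for 1, 2 or 5 held days, against 56–57, 56–58 or 56–61. These figures assume that the patient follows the printed instruction without correction from the site, stops at the last fraction, and has all missed fractions made up at the end.

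The missing rows after Day 38, in both diaries, are a plain gap that needs no assumption beyond one made-up fraction. The Week 6 excess and the resulting threshold shift are possible on one reading only. An effect on DLT classification is plausible in principle, because 6.2 attributes toxicity to the combined treatment, but the documents give no basis for sizing it. For a patient treated without any hold, the two rules give the same 56 doses if dosing stops on Day 38.

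**What to change.** - Reconcile diary instruction 2, footnote B (Schema, 6.1.1 and Section 11) and the Schema column header with Sections 6.1.3.1, 7.2, 7.2.1 and 7.3, so that all give one capecitabine rule. It should cover weekdays without radiation and the end of Week 6. Which rule that is remains for the sponsor and investigators to settle.
- Print that rule in the diary.
- Add rows beyond Day 38 to both diaries for make-up days.
- State one planned capecitabine dose count, and use it for the 67% rule in 6.1.1 and the 80% rule in 6.2.

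The cost is a wording amendment and a reissued diary. No visits, procedures or patients are added.
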